### **1.2.2 Known Potential Benefits**

Flotetuzumab has demonstrated anti-neoplastic activity. During cohort expansion in the CP-MGD006-01 study, 23 patients treated at the threshold 500 ng/kg/day dose have completed at least one cycle of treatment and had a post-treatment bone marrow biopsy. Anti-leukemic activity was documented in 69.5% (16/23) patients, with 4/23 patients achieving CR (2), CRi (1) or PR (1). Additionally, 12 patients had stable disease or other clinical benefits (defined as a decline in bone marrow leukemic blasts not meeting complete or partial response as classified by modified IWG criteria). Additional, recently reported data as of 11/2019 from the same cohort of patients with primary refractory and early relapsed AML treated with target doses of flotetuzumab showed 32.1% (9/28) achieving a CR/CRi. This compares favorably to historic CR/CRi rates of ~12.5% utilizing best SOC options.

### **1.3 Overall Study Design and Plan**

This is an open-label, single-arm, single-center Phase 2 study to evaluate for efficacy, safety and tolerability of flotetuzumab administered as a single agent and/or in combination with DLI in patients with relapsed AML post-allo-HCT.

The study is designed to include 2 cycles of treatment. During Cycle 1, patients will be administered flotetuzumab as a continuous IV infusion with a week 1 ramp up to goal/target dose of 500ng/kg/day, which will be continued for the remaining 21 days of a 28-day (4-week) cycle (Cycle 1). Patients found to meet the primary endpoint of complete remission with incomplete hematologic recovery (CRi) or better on their C1D28 response assessment (bone marrow biopsy) will continue on to Cycle 2 of flotetuzumab administered as a continuous IV infusion at a target dose of 500ng/kg/day for an additional 28-day cycle (Cycle 2). Patients found to be deriving clinical benefit as evidenced by stable disease (SD) or a partial remission (PR) on their C1D28 response assessment (bone marrow biopsy) may also continue to Cycle 2 of flotetuzumab at the same dose at the discretion of the treating physician and investigator. Patients may receive a DLI concurrently with flotetuzumab treatment in Cycle 1 and/or Cycle 2 at the discretion of the investigator and treating physician. DLI, if administered, will be given on or after Day 8 of the respective cycle. Of note, if patients are off flotetuzumab for >72 hours between end of C1 and beginning of C2, they will require repeat week 1 ramp up to goal/target dose of 500ng/kg/day. Patients found to have progressive disease (PD) on their C1D28 response assessment (bone marrow biopsy) will proceed off study with SOC. All patients who receive investigational agent will then be followed for treatment response and safety monitoring.

## 1.4 Study Duration and Dates

It is generally expected that ~15-20 patients will be accrued per year. The target accrual for the study is 25 patients. Therefore, it is anticipated that the time from the study opening to completion of accrual will be ~18 months.

Patients will receive the investigational treatment for the first 28 days of the study (Cycle 1). Based on Day 28 response assessment, patients with CR/CRi/PR/SD may continue investigational treatment for another 28 days (Cycle 2); and patients with PD will come off study. All patients will be followed for 2 years after receiving investigational treatment.

## 1.5 Definition of End of Trial

End of Trial is defined as the date when the last patient on the study completes his or her End of Treatment visit and the last follow-up data is collected.

## 2.0 OBJECTIVES AND ENDPOINTS

Objectives	Endpoints
Primary	
To evaluate the efficacy of flotetuzumab in post-allo-HCT relapsed AML and MDS following Cycle 1 of flotetuzumab (Cycle 1 Day 28 assessment).	Efficacy assessed via composite endpoint of CR and CRi (Cycle 1 Day 28 assessment)
Secondary	

 
• To evaluate the efficacy of flotetuzumab monotherapy in post-allo-HCT relapsed AML and MDS following Cycle 2.
 
• To evaluate the safety and tolerability of flotetuzumab +/- DLI in the post-allo-HCT setting.
 
	
 
• Efficacy assessed at Cycle 2 Day 28 (or at C1 D28 in patients who receive only one cycle):               
 
○ Composite endpoint of CR and CRi at C2 D28
 
○ Overall Response (OR) Rate (defined as PR or greater)
 
○ Morphologic leukemia-free state (MLFS) Rate
 
○ Partial Response (PR) Rate
 
○ Stable Disease (SD) Rate
 
○ Progression Free Survival (PFS)
 
○ Overall Survival (OS)
 
 
 
• Safety and tolerability as assessed by:               
 
○ AE Grading per CTCAE v5.0
 
○ CRS & Neurotoxicity Grading per ASTCT Consensus Guidelines
 
○ Acute GVHD Grading per MAGIC criteria
 
○ Chronic GVHD Grading per NIH severity score
 
 
 

### 3.0 STUDY POPULATION

#### 3.1 Inclusion Criteria

1. Histologically or cytologically confirmed relapsed acute myeloid leukemia (AML) or myelodysplastic syndrome (MDS), including any AML subtype, except acute promyelocytic leukemia (APL), and including AML that has evolved from a previous MDS or MPN.
2. Patients must have peripheral blast count  $\leq 20,000/\text{mm}^3$ . Use of hydroxyurea to control blast count is permitted.
3. Patients must be status post allo-HCT (including: matched related, matched unrelated, haploidentical, mismatched unrelated; and cord blood HCT).
4. Eastern Cooperative Oncology Group (ECOG) performance status (PS)  $\leq 2$  (see Appendix A).
5. Adequate organ function, defined as:
  - a. Hepatic transaminase (both alanine aminotransferase (ALT) and aspartate aminotransferase (AST) levels  $\leq 2.5$  times the institutional upper limit of normal (ULN),
  - b. Total bilirubin level  $\leq 1.5$  times the ULN (unless the patient has a history of Gilbert's Syndrome, in which case, total bilirubin must be  $\leq 2.5$  times the ULN),
  - c. Creatinine clearance of  $\geq 50$  ml/min.
  - d. Adequate organ reserve including cardiovascular (ejection fraction within institutional normal limits), pulmonary (baseline pulmonary function test [PFT]: carbon monoxide diffusion capacity in the lung [DLCO]  $> 50\%$ , forced expiratory volume in 1 second [FEV1]  $> 70\%$ ), renal, and hepatic functioning sufficient, in the judgment of the Investigator, to undergo therapy.
  - e. Normal thyroid function or stable thyroid tests on supplementation, except euthyroid sick syndrome.
6. Recovery from toxicities of clinical consequence attributed to previous chemotherapy to CTCAE v4.0 Grade  $\leq 1$  (i.e., certain toxicities such as alopecia will not be considered in this category).
7. Female patients of childbearing potential must test negative for pregnancy at enrollment and during the study. Sexually active women of child-bearing potential, unless surgically sterile, must be willing to use a highly effective method of birth control defined as those which result in a low failure rate (i.e., less than 1% per year) such as implants, injectables, combined oral contraceptives, intra-uterine devices (IUDs) or vasectomized partner. Male patients with partners of childbearing potential must be either vasectomized or agree to use a condom in addition to having their partners use another method of contraception resulting in a highly effective method of birth control defined as those which result in a low failure rate (i.e., less than 1% per

- year) such as implants, injectables, combined oral contraceptives, or IUDs. Patients should not have sexual intercourse with females who are either pregnant or lactating without a condom. Contraception should be employed from the time of consent through 12 weeks after flotetuzumab administration. Patients should also abstain from sperm/egg donation during the course of the study.
8. Able to have corticosteroids weaned to  $\leq 0.5$ mg/kg prednisone/day (or equivalent)
  9. Able to have non-steroidal immunosuppression discontinued, including:
    - a. mycophenolate (MMF)
    - b. calcineurin inhibitors (tacrolimus, cyclosporine)
      - i. calcineurin inhibitors must be able to be discontinued at least 14 days prior to enrolling on study.
    - c. JAK inhibitors (ruxolitinib)
    - d. MTOR inhibitors (sirolimus)
  10. At least 18 years of age.
  11. Ability to understand and willingness to sign an IRB approved written informed consent document.

### **3.2 Exclusion Criteria**

1. Active GVHD requiring systemic immunosuppression with more than 0.5mg/day prednisone.
2. Currently receiving any other investigational agents.
3. Any active untreated autoimmune disorders (with the exception of vitiligo, resolved childhood atopic dermatitis, prior Grave's disease now euthyroid clinically and with stable supplementation).
4. Second primary malignancy that requires active therapy (adjuvant hormonal therapy is allowed).
5. Antitumor therapy (chemotherapy, radiotherapy, antibody therapy, molecular-targeted therapy, retinoid therapy, or investigational agent) within 5 half-lives of Cycle 1 Day 1.
6. At the time of study entry, steroids  $>0.5$ mg/kg of prednisone or equivalent (except steroid inhaler, nasal spray or ophthalmic solution which are allowed).
7. Use of immunosuppressant medications (other than steroids as noted) in the 2 weeks prior to study drug administration (Cycle 1 Day 1).
8. Isolated extramedullary relapse (i.e., no evidence of bone marrow involvement).

9. Known central nervous system (CNS) leukemia. Patients with suspected CNS leukemia must be evaluated by lumbar puncture and be free of CNS disease prior to study entry. Previously treated CNS leukemia is allowed provided adequate treatment has been provided and the patient is free of CNS disease.
  
10. Any medical or psychiatric condition limiting full compliance or increasing the safety risk, at the discretion of the PI, such as:
  - a. active uncontrolled infection (including, but not limited to viral, bacterial, fungal, or mycobacterial infection),
  - b. known human immunodeficiency virus infection,
  - c. known, active, or chronic hepatitis B or C infection (appropriately treated HBV/HCV infections with documented clearance of viral titer are allowed),
  - d. Grade 3 or 4 bleeding,
  - e. significant pulmonary compromise including chronic supplemental oxygen use, history of non-infectious pneumonitis (including radiation pneumonitis), pulmonary fibrosis, or severe chronic obstructive pulmonary disease (COPD),
  - f. uncontrolled (persistent) hypertension (systolic pressure > 180 mm Hg or diastolic pressure > 100 mm Hg)
  - g. clinically significant arrhythmia, clinically significant baseline QTcF >480 msec,
  - h. unstable angina,
  - i. recent myocardial infarction within 6 months prior to study drug administration (Cycle 1 Day 1),
  - j. clinically significant heart disease, such as, congestive heart failure, history of pericarditis, myocarditis,
  - k. history of stroke or transient ischemic event within 3 months prior to study drug administration (Cycle 1 Day 1),
  - l. untreated pulmonary embolism, or non-catheter-related deep-vein thrombosis in the 3 months prior to study drug administration (Cycle 1 Day 1),
  - m. pregnancy, or breast feeding,
  - n. major surgery or trauma within 4 weeks before enrollment.
  
11. Known hypersensitivity to murine, yeast, or recombinant proteins; polysorbate 80; recombinant human serum albumin; benzyl alcohol; or any excipient contained in the flotetuzumab drug formulation.
  
12. Dementia or altered mental status that would preclude sufficient understanding to provide informed consent.

### **3.3 Inclusion of Women and Minorities**

Both men and women and members of all races and ethnic groups are eligible for this trial.

## **4.0 REGISTRATION PROCEDURES**

**Patients must not start any protocol intervention prior to registration through the Siteman Cancer Center.**

The following steps must be taken before registering patients to this study:

1. Confirmation of patient eligibility
2. Registration of patient in the Siteman Cancer Center database
3. Assignment of unique patient number (UPN)

### **4.1 Confirmation of Patient Eligibility**

Confirm patient eligibility by collecting the information listed below:

1. The registering MD's name
2. Patient's race, sex, and DOB
3. Three letters (or two letters and a dash) for the patient's initials
4. Copy of signed consent form
5. Completed eligibility checklist, signed and dated by a member of the study team
6. Copy of appropriate source documentation confirming patient eligibility

### **4.2 Patient Registration in the Siteman Cancer Center OnCore Database**

All patients must be registered through the Siteman Cancer Center OnCore database.

### **4.3 Assignment of UPN**

Each patient will be identified with a unique patient number (UPN) for this study. All data will be recorded with this identification number on the appropriate CRFs.

### **4.4 Screen Failures**

Screen failures are defined as participants who consent to participate in the clinical trial but are not subsequently randomized to the study intervention or entered in the study. A minimal set of screen failure information is required to ensure transparent reporting of screen failure participants, to meet the Consolidated Standards of Reporting Trials (CONSORT) publishing requirements and to respond to queries from regulatory authorities. Minimal information includes demography, screen failure details, eligibility criteria, and any serious adverse event (if applicable).

## 5.0 STUDY TREATMENT PLAN

### 5.1 Premedication Administration

Due to the risk of infusion-related reactions (IRRs), specific pre-treatment regimens are described below. Table 1 below presents the premedication and prophylaxis regimens.

#### Prior to the first dose (Week 1):

All patients are to be treated as described in Table 1 below. No additional steroids should be administered for infusion-related reaction prophylaxis except as detailed below. Patients should receive adequate hydration during study therapy, and the addition of IV fluids to maintain intravascular volume (e.g., 50-100 mL/hr of normal saline) is recommended for at least 48 hours after the start of therapy.

#### Prior to Week 2 dosing:

The premedication schedule should be followed as described in Table 1 below. In addition, these premedications should be considered after consultation with the Principal Investigator (PI) if patients are resuming flotetuzumab treatment after a dose interruption lasting > 1 day in Cycle 1 or 2:

- Steroids should not be administered for infusion-related reaction prophylaxis except as indicated below, but may be used for the treatment of emerging symptoms as clinically appropriate.
- Tocilizumab (8 mg/kg IV) may be used prophylactically in patients who have had severe IRR or CRS in the first week of dosing upon consultation with the PI.
- Patients should receive adequate hydration during study therapy, and the addition of IV fluids to maintain intravascular volume (e.g., 50-100 mL/hr of normal saline) is recommended for at least 48 hours after the start of therapy in Week 2.

#### Prior to subsequent doses (after Week 2):

1. The premedication schedule should be followed as described in Table 1 below. Tocilizumab or steroids may be considered after consultation with the PI.
2. For infusion-related reactions during the course of treatment, supportive care measures should be implemented as outlined in Section 6.1.
3. IV fluids should be administered for all patients unless contraindicated.

**Table 1: Flotetuzumab Ramp & Continuous Infusion Pre-medications**

28 day continuous Flotetuzumab infusion schedule				
Medication	Week 1	Week 2	Week 3	Week 4
Acetaminophen (1000mg PO)	Day 1 : 30 minutes prior to dosing, then q8 hrs for 48 hours  Day 7 or day of target dose : 30 minutes prior to dose change, then q8 hrs for 48 hours	None	None	None

28 day continuous Flotetuzumab infusion schedule				
Medication	Week 1	Week 2	Week 3	Week 4
Diphenhydramine (25-50mg IV or PO) or equivalent	Day 1 : 30 minutes prior to dosing, then q8 hrs for 48 hours  Day 7 or day of target dose : 30 minutes prior to dose change, then q8 hrs for 48 hours	None	None	None
Ranitidine (50mg IV) or equivalent	Day 1 or day of target dose : 30 minutes prior to dosing, then q8 hrs for 48 hours  Day 7 or day of target dose : 30 minutes prior to dose change, then q8 hrs for 48 hours	None	None	None
Dexamethasone (or equivalent)	Day 1 : 10-20mg IV up to 30 minutes before dosing. Then 4mg IV at 12 hours after dosing.  Day 7 or day of target dose : 10mg IV up to 30 minutes prior to dose change, then 4mg 12 hrs later.	None	None	None
Tocilizumab (8mg/kg IV)	None	After consultation with PI	None	None

## 5.2 Study Intervention Description

Patients enrolled on study will be admitted to the hospital for admission assessments, administered premedications and started on Cycle 1 Day 1 on the dose escalation ramp schedule (Table 3) of flotetuzumab as a continuous IV infusion. During the ramp week, patients will be initiated on flotetuzumab at 30 ng/kg/day and have their flotetuzumab dose increased daily to a target goal of 500 ng/kg/day by Day 7.

Patients will then continue on flotetuzumab continuous IV infusion at 500 ng/kg/day for the remaining 21 days of the 28-day cycle.

On Cycle 1 Day 28, patients will undergo repeat bone marrow biopsy for assessment of disease status. Patients not deriving clinical benefit defined as PD (Table 2) will proceed with SOC therapy off study. Patients who have achieved a CR/CRi will proceed to a second cycle per protocol, while patients deriving clinical benefit defined as PR or SD or better may proceed to Cycle 2 with permission of the investigator. Patients with available donor lymphocytes may receive DLI concurrently with flotetuzumab during Cycle 1 and/or Cycle 2. At the discretion of Principal Investigator, on Cycle 1 Day 14 patients will undergo a bone marrow biopsy for tissue banking and correlative studies.

### 5.2.1 Cycle 1

Cycle 1 will include pre-medications, a dose escalation ramp of flotetuzumab and then a continuous infusion of flotetuzumab (Tables 1 & 3).

- Patients will be admitted to the hospital on day 0 for admission assessments.
- Pre-medications will be administered, beginning on Day 1, as in the previous phase 2 trial NCT02152956.
- The dose escalation ramp will begin on Day 1 and will consist of continuous ramp infusion of flotetuzumab starting at 30 ng/kg/day with increasing dose over 7 days to a target dose of 500 ng/kg/day.
- Patients will then continue on flotetuzumab for additional 21 days at target dose of 500 ng/kg/day (28 days total).
- Patients may receive a DLI at the discretion of the treating physician on or after Day 8 of Cycle 1.
- At mid-Cycle 1 (Day 14), at the discretion of the Principal Investigator, patients will undergo a bone marrow biopsy for correlative studies only (not used for disease response assessments).
- At the end of Cycle 1 (Day 28), patients will undergo bone marrow biopsy for correlative studies **and** disease response assessment.
- Patients not deriving clinical benefit (defined as PD, Table 2) will proceed with SOC therapy off study. Patients with a CR/CRi (Table 2) will proceed to Cycle 2 per protocol. Patients deriving clinical benefit (defined as SD or better, Table 2) may proceed to Cycle 2 with permission of the investigator.

**Table 2: Response Criteria**

Complete remission (CR)	Bone marrow blasts <5%; absence of circulating blasts and blasts with Auer rods; absence of extramedullary disease; ANC $\geq 1.0 \times 10^9/L$ (1000/ $\mu$ L); platelet count $\geq 100 \times 10^9/L$ (100,000/ $\mu$ L), transfusion independence
CR with incomplete hematologic recovery (CRi)	All CR criteria except for residual neutropenia ( $<1.0 \times 10^9/L$ [1000/ $\mu$ L]) or thrombocytopenia ( $<100 \times 10^9/L$ [100,000/ $\mu$ L])
Morphologic leukemia-free state (MLFS)	Bone marrow blasts <5%; absence of blasts with Auer rods; absence of extramedullary disease; no hematologic recovery required
Partial remission (PR)	All hematologic criteria of CR; decrease of bone marrow blast percentage to 5 to 25%; and decrease of pretreatment bone marrow blast percentage by at least 50%
Stable disease (SD)	Absence of CR, CRi, PR, MLFS; and criteria for PD not met
Progressive disease (PD)	Evidence for an increase in bone marrow blast percentage (>50% over baseline), and/or increase of absolute blast counts in the blood (>50% to $>25 \times 10^9/L$ ) without differentiation syndrome, or new extramedullary disease

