### 5.3 Response Assessments

Bone Marrow Biopsy (BM Bx) will be performed at the following timepoints for disease assessments and correlative assessments:

- Screening/Baseline BM Bx: performed prior to starting on treatment.
- Cycle 1 D14 (+/- 3 days) BM Bx mid-Cycle 1 (correlative assessments only, no disease response assessment, collected at PI's discretion only).
- Cycle 1 D28 (+/- 3 days) BM Bx following completion of Cycle 1.
- Cycle 2 D28 (+/- 3 days) BM Bx following completion of Cycle 2.
- Final BM Bx performed at the time of suspected disease relapse or progression.

Responses will be assessed via IWG Criteria (Table 2).

See Section 7.0 for additional details regarding bone marrow biopsy schedule and correlative assessments.

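### Relapse after CR/CRi has no response category, so a relapse found at Cycle 2 Day 28 may be scored SD or PR and is not literally a PFS event

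*Combined protocol and SAP*

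**What the plan says.** Table 2 (under Section 5.2.1) and its copy in Section 10.0 list six categories: CR, CRi, MLFS, PR, SD and PD.

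- **PD, marrow:** "Evidence for an increase in bone marrow blast percentage (>50% over baseline"). Section 5.3 identifies the reference marrow: "Screening/Baseline BM Bx: performed prior to starting on treatment".
- **PD, other routes:** "and/or increase of absolute blast counts in the blood", with a level of 25 × 10⁹/L attached, and "without differentiation syndrome, or new extramedullary disease".
- **PR:** "All hematologic criteria of CR", together with "decrease of bone marrow blast percentage to 5 to 25%; and decrease of pretreatment bone marrow blast percentage by at least 50"%.
- **SD:** whatever is left once CR, CRi, MLFS, PR and PD are excluded.

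Section 2.0 reads the secondary response endpoints at Cycle 2 Day 28 for patients given two cycles, and includes "Overall Response (OR) Rate (defined as PR or greater"). Under Sections 5.2 and 5.2.1, patients in CR/CRi go on to Cycle 2. Section 10.0 ends PFS at disease progression or death, and plans a response duration without saying what ends it. Relapse appears next to progression as a reason for a biopsy: "Final BM Bx performed at the time of suspected disease relapse or progression". It is not defined anywhere as a response category.

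**The concern.** The Cycle 2 Day 28 marrow is the first scheduled response marrow after a Cycle 1 remission, so it is where an early relapse would first be documented. Table 2 does not look back to that remission. It compares the new marrow only with the pretreatment one, and nothing resets the reference to the best response or nadir. A patient who has lost a remission can still have far fewer blasts than at entry, and the table then describes that patient as stable or partially responding.

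At stake are the Cycle 2 Day 28 OR, PR and SD rates, and to a lesser extent MLFS, together with PFS and response duration. PFS and response duration are the plan's measures of durability. Without a rule, two assessors could also score the same marrow differently.

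**Working it through.** The plan states no figure on this point, so the check applies Table 2 literally.

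**Rules.** Let b be the pretreatment marrow blast percentage and r the percentage at Cycle 2 Day 28, for a patient in CR/CRi at Cycle 1 Day 28.

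- Marrow PD: r > 1.5 × b. This cannot be reached once 1.5 × b ≥ 100, that is b ≥ 66.7%.
- PR: 5 ≤ r ≤ 25, r ≤ 0.5 × b, and CR-level counts. This needs 0.5 × b ≥ 5, so b ≥ 10%.
- SD: r ≥ 5 and neither of the above.
- Blood blasts at the PD level, or new extramedullary disease, give PD at any b.

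**Results by baseline** (b and r are illustrative; the documents give no blast distribution; no non-marrow PD criterion met):

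| b (%) | PR if counts held, r (%) | SD, r (%) | Marrow PD, r (%) |
|---|---|---|---|
| 8 | none (0.5 × 8 = 4) | 5 to 12 | above 12 |
| 10 | 5 only | above 5 to 15 | above 15 |
| 20 | 5 to 10 | above 10 to 30 | above 30 |
| 40 | 5 to 20 | above 20 to 60 | above 60 |
| 50 | 5 to 25 | above 25 to 75 | above 75 |
| 80 | 5 to 25 | above 25 | unreachable (1.5 × 80 = 120) |

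If counts are not at CR level, the PR column also becomes SD.

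**Worked case.** Take b = 40%, 2% at Cycle 1 Day 28 (CR), and r = 12% at Cycle 2 Day 28. Since 12 ≤ 20 and 12 lies within 5-25, ANC 1.5 and platelets 110 (× 10⁹/L), with the other CR blood criteria met, give PR and an overall response. With platelets of 60 the result is SD. Marrow PD would need more than 60%.

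**How often, under assumed ranges.** Take b uniform on 10-60 and r uniform on 5-25, a total area of 50 × 20 = 1,000.

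- PD area: ∫ from 15 to 25 of (r/1.5 − 10) dr = 33.3, or 3%.
- PR-range area: ∫ from 10 to 50 of (b/2 − 5) db, plus 10 × 20, = 400 + 200 = 600, or 60%.
- SD: the remaining 37%.

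With b on 20-80 the shares are 0%, 81% and 19%. If r extends to 50%, PD rises to 18% (b on 10-60) or 5% (b on 20-80). With low baselines, b on 5-30, PD is 20% for r up to 25% and 53% for r up to 50%. These shares use marrow values alone. The PR-range share is an upper limit for PR, because the blood-count requirement has not been applied.

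**Size per patient.** 1/25 = 4 percentage points. At the 30% target, 0.30 × 25 = 7.5, so 7 or 8 responders. If 1 or 2 of them relapsed by Cycle 2 Day 28 and were misclassified (an assumption), 4 to 8 points would be wrongly placed across OR/PR and SD together.

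**Marrow below 5%.** If blood blasts return below the PD level while the marrow stays under 5%, the score is MLFS, because that row does not require the absence of circulating blasts.

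**Time to event.** Section 10.0 counts progression or death. A relapse below the PD thresholds is neither, so follow-up for PFS literally continues past it, and no rule closes the response duration.

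**The case against.** Several points on the other side stand.

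- **Not every relapse is scored PR or SD.** A reader might infer this from the missing row. The blood and extramedullary criteria for PD do not depend on the marrow, and a low baseline makes marrow PD easy to reach. MDS is eligible, and at b = 8% anything above 12% is PD and PR is impossible.
- **Counting a relapse as an overall response is the narrower error.** PR needs CR-level counts, including transfusion independence, and a patient with continuing cytopenia cannot meet it. SD is probably the commoner misclassification, and SD does not enter OR.
- **Loss of response is not hidden.** A reader might infer that it is. But a marrow at 5% or more fails CR/CRi under any scoring, so the Cycle 2 Day 28 CR/CRi rate falls as it should. Appendix I also lists each patient's two response assessments side by side.
- **The PR wording can be disputed.** A rise from 2% to 12% is hard to call a decrease to 5-25%. However, the comparator the row names is pretreatment, and if PR is refused the patient falls to SD, which is still not relapse.
- **Intent cannot be proved.** Naming relapse as a biopsy trigger does not show how the authors would score it.
- **The affected analyses are descriptive.** Section 11.7 attaches no test or decision to them.

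These points limit the reach of the defect but do not supply the missing rule. Nor does reading OR as best response: Sections 2.0 and 5.5 tie it to the Cycle 2 Day 28 assessment for two-cycle patients.

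**Conclusion.** The concern holds as a gap in the secondary endpoint definitions and should be corrected. A relapse from CR/CRi may be scored SD, or PR under the conditions above, unless a PD criterion is met. It is also not literally a PFS event and does not end response duration.

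The effect is about 4 percentage points per misclassified patient out of 25 on the descriptive OR, PR and SD rates. The number of such patients, and the split between PR and SD, depend on assumed blast values, blood counts and relapse frequency. Inflation of the OR rate specifically cannot be estimated from the documents.

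A reader might take this as a threat to the main result. The documents do not support that: the primary endpoint is CR/CRi at Cycle 1 Day 28, the futility rule in Section 11.4 counts CR/CRi, and neither uses the PR, SD or PD boundaries at Cycle 2 Day 28.

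**What to change.** Add a relapse row to Table 2 and to its copy in Section 10.0, for endpoint scoring:

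- **After CR or CRi:** marrow blasts of 5% or more, reappearance of blood blasts, or new extramedullary disease.
- **After MLFS:** marrow blasts of 5% or more, or new extramedullary disease only. Blood blasts cannot define relapse here, because MLFS does not require their absence.

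Then state that relapse:

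- takes precedence over MLFS, PR and SD;
- counts as a non-response in the Cycle 2 Day 28 OR rate, and is not counted in the MLFS, PR or SD rates;
- is a PFS event;
- ends response duration.

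The cost is one row in two places and a few sentences, using marrow, blood and extramedullary assessments already planned. The downside is that OR, PR, SD and PFS may look slightly less favourable.
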